## ***8.4 Missing data***

Only observed data will be summarized for all Cohorts. Except for partial or missing dates, no imputation for missing data is planned for the summary or analyses of these study data.

The missing component(s) of incomplete dates (e.g. start and/or stop dates of AE, concomitant medication, medical history) will be assumed as the most conservative value possible. For example, if the start date has a missing day value, the first day of the month will be imputed for study day computations, etc. If day is missing for an end date, the last day of the month will be imputed. If the start date has a missing month value, the first month of the year will be imputed for study day computations, etc. If month is missing for an end date, the last month of the year will be imputed. For determination of treatment-emergent status, the start date will be imputed as the date of the first dose of study drug, unless there is clear evidence (through comparison of partial dates/times) to suggest otherwise.

Date imputation will only be used for computational purposes such as treatment-emergent status, etc. Actual data values, as they appear in the original eCRFs, will be presented in the subject data listings.

QMS Document Name: Statistical Analysis Plan	Page 14 of 29
QMS No (include version ref): STF-015-GL.02	Document date: 09JUL2019
CONFIDENTIAL	

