### **14.1 Adverse Events**

All information obtained on AEs will be displayed by treatment and patient. The number and percentage of subjects with AEs will be tabulated by System Organ Class (SOC) and Preferred Term (PT) with a breakdown by treatment. A patient with multiple AEs events within a SOC is only counted once towards the total of this SOC.

AEs will be coded using MedDRA version 23.1 or higher and presented by SOC and PT.

QMS Document Name: Statistical Analysis Plan	Page 20 of 29
QMS No (include version ref): STF-015-GL.02	Document date: 09JUL2019
CONFIDENTIAL	

The analysis will focus on the treatment-emergent AEs (TEAE), i.e., AEs which started or worsened on or after the study ALM-488 infusion and before the end of the study.

Number and frequencies of subjects with TEAEs as well as the number of events will be given by SOC and by PT within each SOC overall and by individual Cohorts (i.e., Cohorts: A, A1, A2, A3, A4, A5, A6, B, B1, B2) for the following:

- Any AE
- AE type
- At least one TEAE
- Serious TEAEs
- TEAE by CTCAE
- Infusion reactions IR overall and by CTCAE
- Related TEAEs
- Adverse Device Effects
- All TEAEs by maximum intensity

The counts and percentages of subjects with TEAEs as well as number of events will be presented by SOC and by PT and by decreasing frequency for:

- All TEAEs
- IR
- Serious TEAEs.
- Related TEAEs
- Serious Related.
- TEAEs leading to study discontinuation (if occurring in more than 5 subjects, otherwise a listing will be sufficient)
- Adverse Device Effects
- All TEAEs by intensity.
- All related TEAEs by intensity
- All TEAEs by outcome

Additionally, number and frequencies of subjects with TEAEs and number of events will be presented by PT and by decreasing frequency for

- All TEAEs
- Serious TEAEs
- Related TEAEs.

QMS Document Name: Statistical Analysis Plan	Page 21 of 29
QMS No (include version ref): STF-015-GL.02	Document date: 09JUL2019
CONFIDENTIAL	

Finally, a summary of Serious TEAEs and deaths by individual Cohorts and for all patients

Listings will be created for

- All AEs
- Serious AEs (SAEs)
- AEs leading to discontinuation of study medication
- AEs leading to discontinuation from study
- AEs leading to death

and will also include subjects screened but not infused with ALM-488.

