If severity is missing, the event will not be included in the frequency tables presenting events by intensity. If relationship to study drug is missing, the event will be assessed as unrelated if it started before start of study medication; in all other cases it will be assumed to be related.

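### TEAEs with missing severity are dropped from the by-intensity tables, so those tables may not reconcile with the all-TEAE tables and a subject's maximum intensity can be understated

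*SAP*

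**What the plan says.** The rule for missing severity is in SAP Section 14.1: "If severity is missing, the event will not be included in the frequency tables presenting events by intensity". The same section plans three outputs that depend on severity:

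- "All TEAEs by maximum intensity", in the list of summaries given overall and by cohort. Section 20.1 lists no table with maximum intensity in its title, so the output that will carry it is not identified.
- All TEAEs by intensity (Table 14.3.1.9).
- "All related TEAEs by intensity" (Table 14.3.1.10).

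The last two belong to a list of tables, sorted by how common the events are, that count both subjects and events.

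Three other provisions bear on the point:

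- For missing relationship to study drug, Section 14.1 treats an event with onset before dosing as unrelated; otherwise, "in all other cases it will be assumed to be related".
- Section 8.4 states the general policy: "Except for partial or missing dates, no imputation for missing data is planned for the summary or analyses of these study data".
- Section 8.1 says that tables of categorical variables will also show how many subjects have missing values.

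Section 14.1 itself gives no missing category, worst-case count or sensitivity display for ungraded events.

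**The concern.** Safety is the primary objective, and the adverse event tables are read cohort by cohort, with 3 to 6 subjects per dose level. Under the stated rule an ungraded TEAE is counted in the all-TEAE table but not in the by-intensity table, and Section 14.1 provides no line to account for the difference. Unless the table shells add one, a subject whose only TEAE is ungraded has no entry in the intensity table. A subject with one mild and one ungraded event is shown as mild at most. The effect on maximum intensity runs in one direction only.

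The treatment of related events is also uneven. Suppose a TEAE starts after dosing and lacks both severity and relationship. It is counted as related in Table 14.3.1.5, because "in all other cases it will be assumed to be related", but it is absent from related TEAEs by intensity in Table 14.3.1.10.

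**Working it through.** **Denominators (SAP Section 4.1).** Escalation/de-escalation: 3 cohorts × 3 = 9 to 6 cohorts × 6 = 36. Timing: 2 × 6 = 12. Totals: 9 + 12 = 21 and 36 + 12 = 48. All agree with the SAP. Sections 5 and 14 assign safety analyses to the Safety Analysis Set (SAF). Section 14.1 states no denominator for the intensity tables, so the number of SAF subjects in the cohort is assumed below.

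**Direction.** The maximum over a subset of a subject's events cannot exceed the maximum over all of them. Dropping ungraded events can therefore lower a subject's displayed maximum or leave it unchanged, but cannot raise it. Illustration: a subject has a grade 1, a grade 2 and an ungraded event. Under the rule the intensity table shows 2 events and maximum grade 2, while the all-TEAE table shows 3 events. If the ungraded event were grade 3 (assumed for illustration), the true maximum would be 3.

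**Size, if one subject is affected.** Take a cohort in which one subject's only TEAE is ungraded and no other subject is in the top category. The table compares the rule with a worst-case count, using exact (Clopper-Pearson) 95% intervals.

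| n | Under the rule | Worst-case count | Shift, 1/n |
|---|---|---|---|
| 3 | 0/3 = 0% (0 to 70.8) | 1/3 = 33.3% (0.8 to 90.6) | 33.3 points |
| 6 | 0/6 = 0% (0 to 45.9) | 1/6 = 16.7% (0.4 to 64.1) | 16.7 points |
| 12 | 0/12 = 0% (0 to 26.5) | 1/12 = 8.3% (0.2 to 38.5) | 8.3 points |
| 48 | 0/48 = 0% (0 to 7.4) | 1/48 = 2.1% (0.1 to 11.1) | 2.1 points |

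These are upper limits for one subject. If the ungraded event does not change the subject's category, the shift in that category is zero.

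**How likely is a dropped event?** The documents give neither a missing-severity rate nor an expected number of TEAEs, so both are assumed. With E events, each missing severity independently with probability m, the chance that at least one is dropped is 1 − (1 − m)^E.

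| E | m = 1% | m = 5% |
|---|---|---|
| 10 | 9.6% | 40.1% |
| 50 | 39.5% | 92.3% |
| 100 | 63.4% | 99.4% |

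**The SAP's own conventions side by side.**

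- Section 8.1 displays missing values for categorical variables, and Section 14.3 gives qualitative laboratory results a missing category. Section 14.1 says only that the ungraded event is left out.
- Section 8.4 bars imputation except for dates. Leaving severity unimputed fits that policy, and so would a missing row, which imputes nothing. The relationship rule in Section 14.1 does impute, so it is already an exception.

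**The case against.** The strongest defence is that nothing is lost from the safety record. The exclusion is confined to tables by intensity. The event still counts in the overview (14.3.1.1) and the SOC/PT table (14.3.1.2), in the serious, related and outcome tables where applicable, and in the adverse event listings. With 21 to 48 subjects, comparing 14.3.1.9 with 14.3.1.2 would expose any gap. Section 8.1 may also already require a missing count, and the table specifications are in a separate document (Section 2.1) that may provide one. All of this stands and limits the importance of the point. It does not settle whether the specific sentence in Section 14.1 overrides Section 8.1, and finding a gap by comparing two tables is a poor substitute for a row that explains it.

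A reader might infer more than the documents support:

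- *That the rule always makes the drug look milder.* It does not. Dropping an event that was truly mild leaves the severe count unchanged and raises the severe share among graded events. Only the statement about maximum intensity is one-directional.
- *That it is the exact opposite of a worst-case rule for causality.* The relationship rule is not uniformly worst case. TEAEs are "AEs which started or worsened on or after the study ALM-488 infusion and before the end of the study", so an event that began before dosing and worsened afterwards is a TEAE, yet with missing relationship it is set to unrelated. The contrast holds only for events starting on or after dosing.
- *That every severity display is affected.* Section 14.1 also plans TEAEs and infusion reactions by CTCAE, and it does not say whether these count as tables by intensity.
- *That dose selection is put at risk.* Sections 4, 4.1 and 12 rest the Optimal Dose on DLTs, adequacy of fluorescence and SRC review, with a separate DLT plot and listing. No route from an intensity table to that decision is described.
- *That ungraded events should simply be counted as severe.* For one possibly trivial event this would add 33 points to the severe rate of a 3-subject cohort, which is the same distortion reversed, and it would conflict with Section 8.4.

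**Conclusion.** The point holds in limited form. Followed literally, Section 14.1 can leave the by-intensity tables short of the all-TEAE totals and can understate, but not overstate, a subject's maximum intensity. The shift from one affected subject is at most 33 percentage points at n=3, 17 at n=6 and 8 at n=12. This rests on three assumptions: at least one TEAE lacks a severity, the ungraded event changes the subject's category, and the denominator is the number of SAF subjects in the cohort. The chance of a dropped event cannot be derived from the documents, and the range shown depends on assumed inputs. The impact is modest, because the tables are descriptive, the events appear elsewhere, and dose selection does not rest on these tables. It still merits correction: the rule bears on the primary objective, cohorts are very small, and the remedy is nearly free.

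**What to change.** Replace the sentence on missing severity in SAP Section 14.1 with text to this effect:

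> TEAEs with missing severity will be kept in every table by intensity under a 'Missing' row, so that totals agree with the corresponding table not split by intensity. The maximum-intensity summary will show the observed result and, beside it, a count in which ungraded TEAEs are placed in the worst-case category. The second count is a sensitivity display and an exception to the no-imputation rule in Section 8.4.

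Three details complete the change:

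- Name the worst-case category, because Section 14.1 neither lists the intensity categories nor maps them to CTCAE grade.
- State whether the by-CTCAE outputs follow the same rule.
- Cross-refer Sections 8.1, 8.4 and 14.1 so that they agree.

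The observed result stays primary, and 'severe' is not imputed in it. The cost is a short SAP edit, one row in Tables 14.3.1.9 and 14.3.1.10, and one column in the maximum-intensity summary. The downside is that some rates may look slightly less favourable.

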#### **14.2 Vital Signs**

The actual values and the change from baseline in vital signs will be summarized over time with n, mean, standard deviation, and median, minimum, and maximum.

Vital signs i.e. height, weight, systolic blood pressure, diastolic blood pressure, heart rate, and respiratory rate will be summarized descriptively over time by individual Cohorts (i.e., Cohorts: A, A1, A2, A3, A4, A5, A6, B, B1, B2).

Furthermore, the number and percentage of subjects based on reference ranges will be described according to the derived categories (i.e. Low, Normal, High) for vital signs.

A listing of vital signs will be presented for all measurements

#### **14.3 Clinical Laboratory evaluations**

##### **Hematology, Clinical Chemistry, and Coagulation, Urinalysis**

All laboratory data will be listed by individual cohort, patient and time point and if normal ranges are available abnormalities will be flagged. Summary statistics will be provided by study dose and time point.

The Hematology parameters include: red blood cells, hemoglobin, hematocrit, mean corpuscular volume, mean corpuscular hemoglobin, mean corpuscular hemoglobin concentration, white blood cells, neutrophils, eosinophils, basophils, lymphocytes, monocytes, %neutrophils, %eosinophils, %basophils, %lymphocytes, %monocytes.

The clinical chemistry parameters include: alkaline phosphatase, AST/SGOT, ALT/SGPT, total bilirubin, calcium, phosphorus, blood urea nitrogen, creatinine, GFR, total protein, albumin, glucose, potassium, sodium, chloride, magnesium, bicarbonate, uric acid, lactate dehydrogenase.

Coagulation parameters include: PT, aPTT, INR.

The urinalysis analysis will include protein, blood, leukocytes, glucose, ketones and pH.

QMS Document Name: Statistical Analysis Plan	Page 22 of 29
QMS No (include version ref): STF-015-GL.02	Document date: 09JUL2019
CONFIDENTIAL	

Quantitative data will be examined for trends using descriptive statistics (number of patients with data, number of patients with missing values, mean, standard deviation, median, minimum, and maximum) of actual values and changes from baseline to each visit/time point. This will be presented by individual Cohorts (i.e., Cohorts: A, A1, A2, A3, A4, A5, A6, B, B1, B2).

Quantitative data based on reference ranges will be described according to the NCI-CTCAE version 5.0 grade at each visit over time and by individual Cohorts (i.e., Cohorts: A, A1, A2, A3, A4, A5, A6, B, B1, B2).

Qualitative data will be described according to the categories (i.e. Normal; Abnormal, Not clinically significant; Abnormal, Clinically significant; Missing) and by individual Cohorts (i.e., Cohorts: A, A1, A2, A3, A4, A5, A6, B, B1, B2).

Shift tables of quantitative data showing changes with respect to the normal range and clinical significance between baseline and endpoint post-baseline visits as well as the worst value at any post-baseline visit.

Shift tables of qualitative data showing changes between baseline and post-baseline visits.

Data from unplanned determinations, i.e. usually determinations where the investigator felt follow-up (FU) was necessary, will be included in the number and frequency counts of clinically significant values. They will also be included in the data listings.

A listing of laboratory values will be presented for all measurements and for abnormal findings, i.e. measurements outside of reference ranges. Laboratory values that are outside of reference ranges will be flagged in the data listings, along with corresponding reference ranges.

Shift tables showing changes with respect to toxicity grade according to NCI-CTCAE version 5.0 will be listed using the worst grade.

Laboratory values will be listed by timepoint (screening, prior to ALM-488 infusion (baseline), after ALM-488 infusion, Day 15, Day 28), overall and by individual Cohorts (i.e., Cohorts: A, A1, A2, A3, A4, A5, A6, B, B1, B2) and for all patients.

Data from unplanned visits will not be summarized but will be included in the data listings.

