**SAFETY: LABORATORY PARAMETERS**  
 Table 14.3.3.1.1 Laboratory Parameters (Quantitative), Cohort A Analysis set: SAF  
 Table 14.3.3.1.2 Laboratory Parameters (Quantitative), Cohort B Analysis set: SAF  
 Table 14.3.3.2.1 Laboratory Parameters (Quantitative) by Derived Categories, Cohort A Analysis Set: SAF  
 Table 14.3.3.2.2 Laboratory Parameters (Quantitative) by Derived Categories, Cohort B Analysis Set: SAF  
 Table 14.3.3.3.1 Laboratory Parameters (Qualitative), Cohort A Analysis Set: SAF  
 Table 14.3.3.3.2 Laboratory Parameters (Qualitative), Cohort B Analysis Set: SAF  
 Table 14.3.3.4.1 Laboratory Parameters (Quantitative) – Shift Table Regarding Reference Ranges and Clinical Significance, Cohort A Analysis Set: SAF  
 Table 14.3.3.4.2 Laboratory Parameters (Quantitative) – Shift Table Regarding Reference Ranges and Clinical Significance, Cohort B Analysis Set: SAF  
 Table 14.3.3.5.1 Laboratory Parameters (Qualitative) – Shift Table, Cohort A Analysis Set: SAF  
 Table 14.3.3.5.2 Laboratory Parameters (Qualitative) – Shift Table, Cohort B Analysis Set: SAF  

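### SAP 14.3 both counts and excludes clinically significant laboratory values from follow-up tests at unplanned visits, and leaves their place in the worst-value outputs unclear

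*SAP*

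**What the plan says.** All the relevant laboratory rules are in SAP 14.3.

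- **Counts of clinically significant values.** Unplanned determinations, described as "usually determinations where the investigator felt follow-up (FU) was necessary", "will be included in the number and frequency counts of clinically significant values". They also go into the listings.
- **Unplanned visits.** The section ends: "Data from unplanned visits will not be summarized but will be included in the data listings".
- **Worst value.** Quantitative shift tables run from baseline to post-baseline visits, "as well as the worst value at any post-baseline visit".
- **Worst grade.** Shifts in CTCAE grade "will be listed using the worst grade".
- **Clinical significance.** Qualitative results use the categories "Normal; Abnormal, Not clinically significant; Abnormal, Clinically significant; Missing". In SAP 20.1 the quantitative shift tables are titled "Shift Table Regarding Reference Ranges and Clinical Significance".

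SAP 8.7 adds two general rules. Data are analysed by the visit category held in the database, and dates are not used to move an assessment to another visit. The visits it lists are screening, baseline (Day 1), Day 15 or early termination, and Day 28 or end of study. No unplanned visit is listed.

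**The concern.** Safety is the primary objective, and laboratory evaluations are a named safety endpoint (SAP 6.1 and 7.1). A follow-up test that an investigator orders out of concern is among the results most likely to show a transient abnormality. If the closing sentence of 14.3 is programmed as written, such a result appears in a listing but in no summary table. If the earlier sentence is programmed, it is counted. Two programmers working from the same SAP could therefore produce different safety tables, each able to point to a sentence in support.

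**Working it through.** No power or error-rate calculation applies. The check sets the rules against one case: a laboratory test done at an unplanned visit after infusion and judged clinically significant.

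**1. Count of clinically significant values.** The sentence on unplanned determinations puts the value in. A number or frequency count is a summary, so the closing sentence takes it out. Neither sentence refers to the other. This is a direct conflict.

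**2. Can the value be treated as belonging to a planned visit?** Not by date, because SAP 8.7 rules out reassigning visits by date. The case is also a realistic one. The laboratory time points in 14.3 are screening, before infusion, after infusion, Day 15 and Day 28. With the Day 15 window of ±8 days, the earliest planned sample after the post-infusion one is at Day 15 − 8 = Day 7, early termination aside. A follow-up test in that interval need not fall on any planned visit.

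**3. Worst post-baseline value.** The phrase covers any post-baseline visit. It could take in unplanned visits, or it could mean only the visits listed in SAP 8.7. The sentence does not mention unplanned data. This is an ambiguity, not a contradiction.

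**4. Worst CTCAE grade.** The text calls these outputs shift tables but says they will be listed, and SAP 20.1 has no numbered table titled as a CTCAE shift. If the output is a listing, the closing sentence keeps unplanned values in it. If it is a table, the closing sentence drops them. This too is an ambiguity.

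**5. Where it could show.** Outputs that carry clinical significance are exposed: the quantitative shift tables named above, and the qualitative tables such as "Table 14.3.3.3.1 Laboratory Parameters (Qualitative), Cohort A Analysis Set: SAF", through the categories in 14.3. SAP 20.1 does not say which table holds the clinically significant counts, so this identifies places to check and is not a tally.

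**6. Weight of one subject.** With n subjects in a column, one reclassified subject moves a percentage by 100/n points.

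| Column | n | 100/n |
|---|---|---|
| Dose level, smallest | 3 | 33.3 |
| Dose level, largest; each timing cohort | 6 | 16.7 |
| Cohort B overall | 12 | 8.3 |
| Cohort A overall, smallest | 9 | 11.1 |
| Cohort A overall, largest | 36 | 2.8 |

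The sample sizes are from SAP 4.1. The same weights apply to any one-subject change in any table, so they show how sensitive small columns are and do not measure this conflict. A subject-level percentage changes only if the unplanned value is the subject's only clinically significant one, or is in a worse category than every planned post-baseline value.

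**The case against.** The strongest reply is that the two sentences can be reconciled. They use different terms, determinations and visits, and the first could mean repeat tests at planned visits. Alternatively, the first is a specific rule for one count and the last a general rule that follows directly on the by-time-point listing, so the specific rule could be read as an exception. Both readings are workable, and the second is probably what was meant. But the SAP states neither. Follow-up tests are not confined to planned visits, and the closing sentence has no exception. The reply shows that the repair is easy, not that the text is consistent.

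A second reply concerns reach. A reader might infer that 14.3 expressly includes unplanned values in the worst post-baseline value, so that a third statement joins the conflict. The text does not support that: unplanned data are not mentioned there, and SAP 8.7 lists only scheduled visits. A reader might also want to say how many of the laboratory tables are affected. That cannot be settled, because the tables holding the counts are not identified and the qualitative shift tables could arguably be added.

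A third reply is that little depends on it. This stands in large part. All values, and separately all out-of-range values, remain in the listings; the laboratory outputs are descriptive; and SAP 12 selects the dose on DLTs and fluorescence. The separate table specification (SAP 2.1) may already settle the programming, and it was not available. These points limit the importance of the conflict, but the SAP would still contradict itself.

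**Conclusion.** The conflict over counts of clinically significant values is real and rests on the text alone. For the worst post-baseline value and the worst CTCAE grade, the SAP is ambiguous and needs a stated rule.

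If the closing sentence is applied literally, the direction for post-baseline outputs is one-sided: leaving out values can lower a count or make a worst value milder, and cannot do the reverse. The size is unknown. It depends on how often unplanned visits occur and how often they yield the decisive value, and the documents give neither.

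It would go too far to infer that safety will be under-reported, or that dose selection is compromised. The first is a risk under one of two readings. The second has no support, since SAP 12 does not use these tables. SAP 17 sends selected outputs to the IDMC after each cohort, but the charter naming them was not available, so no effect on safety monitoring is claimed. The correction should be made before the tables are programmed, because it is cheap and concerns the primary objective.

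**What to change.** Replace the last sentence of SAP 14.3 with:

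> Data from unplanned visits will be excluded from by-visit descriptive statistics but will be included in the counts of clinically significant values, the worst post-baseline value and the worst post-baseline CTCAE grade, and in the data listings.

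Use one term, either determinations or visits, in both places, and carry the rule into the separate table specification. The cost is one SAP sentence and a flag in the table programs; the data are already collected and listed.

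Do not add a clause that lets an unplanned value serve as baseline. SAP 8.6 sets baseline as the last value before incision, while 14.3 labels the pre-infusion time point as baseline. In the timing cohorts ALM-488 is given 1-3 or 3-5 hours before surgery, so under 8.6 an unplanned value taken after infusion but before incision could become baseline and hide a change. Those two definitions must be reconciled separately.
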